14.13 Appendix M – MDS-UPDRS

A compléter à Baseline, Visite 3 et Visite 4.

MDS UPDRS I-IV

Source principale d'information :

- patient
- □ aidant
- patient et aidant en proportion égale

Partie I : expérience non motrice de la vie quotidienne

1.1	Altération cognitive	_	
-----	----------------------	---	--

Prendre en compte tous types de niveau d'altération des fonctions cognitives, y compris le ralentissement cognitif, l'altération du raisonnement, la perte de mémoire, les déficits de l'attention et de l'orientation. Evaluer leur impact sur les activités de la vie quotidienne telles qu'elles sont perçues par le patient et/ou l'aidant.

(au cours de la semaine précédente, avez-vous eu des problèmes pour vous rappeler des choses ; pour suivre des conversations, pour fixer votre attention, pour avoir des pensées claires ou pour trouver votre chemin dans la maison ? si oui, l'examinateur demande au patient ou à l'aidant de donner des détails et des approfondissements pour information)

0 = normal : pas d'altération cognitive
1 = minime : altération appréciée par le patient ou l'aidant sans interférence concrète avec l'aptitude du patient à mener des activités et des interactions sociales
2 = léger : dysfonctionnement cognitif cliniquement évident, mais avec seulement des interférences minimes avec l'aptitude du patient à mener des activités et des interactions sociales normales.
3 = modéré : les déficits cognitifs interfèrent mais n'empêchent pas l'aptitude du patient à mener des activités et des interactions sociales normales.
4 = sévère : le dysfonctionnement cognitif empêche l'aptitude du patient à mener des activités et des interactions sociales normales.

1.2 Hallucinations et psychose

Considérer à la fois les illusions (interprétations erronées de stimuli réels) et les hallucinations (fausses sensations spontanées). Considérez tous les principaux domaines sensoriels (visuel, auditif, olfactif, gustatif). Déterminez la présence de sensations non formées, aussi bien que des sensations formées. Evaluez la capacité du patient à critiquer ses hallucinations et identifiez l'existence d'illusions et des pensées psychotiques.

1 1

(au cours de la semaine précédente, avez-vous vu, entendu, senti ou ressenti des choses qui n'existaient pas réellement)

- 0 = normal : pas d'hallucinations, ni de comportement psychotique
- 1 = minime : illusions ou hallucinations non formées, mais le patient les reconnaît et les critique
- 2 = léger : hallucinations structurées indépendantes des stimuli environnementaux. pas de perte de sens critique à leur égard
- 3 = modéré : hallucinations structurées non critiquées par le patient
- 4 = sévère : le patient a des idées délirantes ou paranoïaques

1_1

1.	3 I	Humeur dé	рге	ssive				
Considérez la baisse de l'humeur, la tristesse, la désespérance, les sentiments de vide ou la perte de plaisir. Déterminez leur présence et leur durée pendant la période de la semaine précédente et évaluez leur interférence avec l'aptitude du malade à mener sa routine quotidienne et à participer à des interactions sociales. (au cours de la semaine précédente, vous êtes-vous sentie sans ressort, triste, désespéré(e) ou incapable d'apprécier les choses ? si oui ce sentiment durait-il plus d'un jour à la fois ?rendait-il difficile pour vous le fait de mener vos activités et d'être avec les autres ?)								
0	=	normal	:	pas d'humeur dépressive				
1	=	minime	:	épisodes d'humeur dépressive ne durant pas plus d'un jour à la fois. Pas d'interférence avec l'aptitude du patient à mener des activités et des interactions				
2	=	léger	:	humeur dépressive durant plusieurs jours, mais sans interférence avec des activités et des interactions sociales normales				
3	=	modéré	:	humeur dépressive interférant avec l'aptitude du patient à mener des activités et des interactions sociales normales				
4	=	sévère	:	humeur dépressive empêchant l'aptitude du patient à mener des activités et des interactions sociales normales				

1.4 Etat anxieux

Déterminez les sensations de nervosité, de tension, d'inquiétude ou d'anxiété (incluant les attaques de panique) au cours de la semaine précédente et évaluez leur durée et les interférences avec l'aptitude du patient à mener des activités journalières et à participer à des interactions sociales.

(au cours de la semaine précédente, vous êtes-vous senti(e), nerveux, inquiet(e), tendu(e) ? si oui, ce sentiment durait- il plus d'1 jour à la fois. Est-ce que cela a constitué pour vous une difficulté pour suivre vos activités habituelles ou peut-être avec d'autres personnes)

0 1	=	normal minime	:	pas de sentiment d'anxiété sentiments anxieux présents, mais ne durant pas plus d'un jour à la fois. Pas d'interférence avec l'aptitude du patient à mener des activités et des interactions sociales normales.
2	=	léger	:	sentiments anxieux persistant plus d'un jour à la fois, mais sans interférence avec l'aptitude du patient à mener des activités et des interactions sociales
3	=	modéré	1	sentiments anxieux interférant avec, mais n'empêchant pas l'aptitude du patient à mener des activités et des interactions sociales normales
4	=	sévère	:	sentiments anxieux empêchant l'aptitude du patient à mener des activités et des interactions sociales normales

1.5 Apathie

Déterminez le niveau d'activité spontanée, d'assurance, de motivation et d'initiative, et évaluez l'impact d'une réduction de performance sur les activités quotidiennes routinières et les interactions sociales

(au cours de la semaine précédente, vous êtes-vous senti(e)indifférent à faire des activités ou à être avec des gens ?)

0	=	normal	2	pas d'apathie
1	=	minime	:	l'apathie est perçue par le patient et/ou aidant, mais sans interférence avec les activités quotidiennes ni les interactions sociales
2	=	léger	2	l'apathie interfère avec des activités et des interactions sociales isolées
3	=	modéré	2	l'apathie interfère avec la plupart des activités et des interactions sociales
4	=	sévère	2	attitude passive et retirée, avec perte totale d'initiative

1.6 Signes de syndrome de dysrégulation dopaminergique							
Déterminez la participation du malade à diverses activités par ex une passion atypique ou excessive du jeu, des pulsions ou des intérêts sexuels atypiques ou excessifs, ainsi qu'à d'autres activités répétitives, ou à la prise des médicaments non prescrits sans raison clinique. Evaluez l'impact de telles activités ou comportements anormaux sur la vie personnelle du patient et sur celle de sa famille et de ses relations sociales (emprunter de l'argent, conflits familiaux majeurs, perte d'une partie du temps de travail, sauter des repas ou manquer de sommeil en raison de ces activités. (au cours de la semaine précédente, avez-vous ressenti(e) des fortes pulsions inhabituelles que vous avez eues du mal à contrôler ? vous êtes-vous poussé(e)) faire ou penser des choses et éprouvez-vous de la difficulté à les arrêter ?)							
0	=	normal		pas de problème présent			
1	=	minime	÷	des problèmes existent mais n'entraînent habitu ou la famille/l'aidant	ellement pas de difficulté pour le patient		
2	=	léger	1	des problèmes existent et entraînent habituellen vie personnelle du patient et sa vie de famille	nent quelques difficultés dans la		
3	=	modéré	1	des problèmes existent et entraînent habituellen vie personnelle du patient et sa vie de famille	nent beaucoup de difficultés dans la		
4	=	sévère	:	des problèmes existent et empêchent l'aptitude de interactions sociales normales, ou de mainter vie personnelle et familiale	du patient à mener des activités et nir les standards antérieurs de sa		
1.	7 F	Problème	s de	sommeil	_		
Au cours de la semaine précédente, avez-vous rencontré des problèmes pour vous endormir la nuit ou pour rester endormi pendant la nuit ?prenez en compte la façon dont vous vous êtes senti(e)reposé(e) après vous être réveillé(e) le matin							
0	=	normal	÷	pas de problème des problèmes de sommeil sont présents mais r	n'entraînent nas habituellement		

U	-	normai	- 2 -	pas de probleme
1	=	minime	1	des problèmes de sommeil sont présents mais n'entraînent pas habituellement de difficultés à avoir une nuit complète de sommeil
2	=	léger	:	des problèmes de sommeil entraînent habituellement quelques difficultés à avoir une nuit complète de sommeil
3	=	modéré	1	des problèmes de sommeil entraînent beaucoup de difficultés à avoir une nuit complète de sommeil, mais je dors encore habituellement plus de la moitié de la nuit
4	=	sévère	1	je ne dors habituellement pas la plus grande partie de la nuit

1.8 Somnolence diurne	_
Au cours de la semaine précédente, avez-vous rencontré des prob journée ?	lèmes pour rester éveillé(e)pendant la

0 = normal : pas de somnolence diurne
 1 = minime : une somnolence diurne apparaît mais je peux résister et rester éveillé(e)
 2 = léger : je m'endors parfois quand je suis seul et au repos. Par exemple, pendant que je lis ou en regardant la télévision
 3 = modéré : je m'endors parfois alors que je ne devrais pas. Par exemple, en mangeant ou en parlant à d'autres personnes
 4 = sévère : je m'endors souvent alors que je ne devrais pas. Par exemple, en mangeant ou en parlant à d'autres personnes

1.9 Douleurs et autres sensations

Au cours de la semaine précédente, avez-vous eu des sensations inconfortables dans votre corps telles que douleur, courbatures, fourmillements ou crampes ?

0	=	normal	1	pas de sensations inconfortables
1	=	minime	:	je ressens ces sensations. Cependant, je peux faire les choses et être avec d'autres personnes sans difficulté
2	=	léger	:	ces sensations me procurent quelques problèmes quand je fais des choses et quand je suis avec d'autres personnes
3	=	modéré	:	ces sensations me procurent beaucoup de problèmes, mais ne m'empêchent pas d'effectuer des choses ou d'être avec d'autres personnes
4	=	sévère	:	ces sensations m'empêchent de faire des choses et d'être avec d'autres

1.10 Problèmes urinaires

Au cours de la semaine précédente, avez-vous eu des difficultés à contrôler vos urines ? par exemple, besoin urgent d'uriner, besoin d'uriner trop souvent ou accidents urinaires

0	=	normal	5	pas de problème urinaire
1	=	minime	:	j'ai besoin d'uriner souvent ou urgemment. Cependant, ces problèmes ne causent pas de difficultés dans mes activités quotidiennes
2	=	léger	1	les problèmes urinaires causent quelques difficultés dans mes activités quotidiennes. Cependant je n'ai pas d'accidents urinaires
3	=	modéré	:	les problèmes urinaires causent beaucoup de difficultés dans ma vie quotidienne, incluant des accidents urinaires
4	=	sévère	:	je ne peux pas contrôler mes urines, et utilise une garniture de protection ou une sonde urinaire

1.11 Problèmes de constipation

Au cours de la semaine précédente, avez-vous eu des problèmes de constipation entraînant des difficultés à aller la selle ?

0 1	=	normal minime	:	pas de constipation j'ai été constipé(e). Je fais des efforts supplémentaires pour aller à la selle. Cependant ce problème ne perturbe pas mes activités ou mon confort
2	=	léger	2	la constipation me pose quelques difficultés à faire des choses ou à me sentir confortable
3	=	modéré	:	la constipation me pose beaucoup de problème à faire les choses ou à me sentir confortable. Cependant, elle ne m'empêche pas de faire quoi que ce soit
4	=	sévère	:	j'ai habituellement besoin de l'aide physique d'un tiers pour aller à la selle

1.12 Sensation de tête vide au lever

Au cours de la semaine précédente, avez-vous eu une sensation d'évanouissement, de vertige, de brouillard lorsque vous vous levez d'une position assise ou couchée ?

0 1	=	normal minime	:	pas de sensation de vertige ou de brouillard des sensations de vertige ou de brouillard surviennent. Cependant elles ne me causent pas de problèmes à faire les choses
2	=	léger	:	des sensations de vertige ou de brouillard m'obligent à me tenir à quelque chose, mais je n'ai pas besoin de m'asseoir ou de me recoucher
3	=	modéré	:	des sensations de vertige ou de brouillard m'obligent à m'asseoir ou à me coucher pour éviter de m'évanouir ou de tomber
4	=	sévère	:	des sensations de vertige ou de brouillard me conduisent à tomber ou à m'évanouir

1.13 Fatigue	_

Au cours de la semaine précédente, vous êtes-vous senti(e) habituellement fatigué(e) ? ce sentiment ne fait pas partie du fait d'avoir sommeil ou d'être triste

0	=	normal	2	pas de fatigue
1	=	minime	1	la fatigue se présente. Cependant, elle ne me cause pas de problème à faire les choses ou à être avec les gens
2	=	léger	:	la fatigue me cause quelques problèmes à faire les choses ou à être avec les gens
3	=	modéré	:	la fatigue me cause beaucoup de problèmes à faire les choses ou être avec les gens. Cependant, elle ne m'empêche pas à faire quoi que ce soit
4	=	sévère	1	la fatigue m'empêche de faire des choses ou d'être avec des gens

Partie III : examen moteur en ON

3a : Le patient reçoit-il des médicaments pour traiter les symptômes de la maladie de Parkinson ?

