	Change from baseline to Week 12 (Visit 3) in Stance Time Variability assessed during the 6MWT.
	Secondary Endpoints
	• Rate of falls at Week 12 based on the results of the falls diary.
	• Change from baseline to Week 12 (Visit 3) in the asymmetry of the swing duration assessed during the 6MWT.
	• Change from baseline to Week 12 (Visit 3) in the Mini-BESTest.
	• Change from baseline to Week 12 (Visit 3) in Unified Parkinson's Disease Rating Scale (MDS-UPDRS) Part III sub-score.
	• Change from baseline to Week 12 (Visit 3) in the results of the Parkinson Disease Questionnaire (PDQ-39).
	Exploratory Endpoints
	• Rate of falls at Week 24 based on the results of the falls diary.
	• Change from Baseline to Week 24 (Visit 4) and from Week 12 (Visit 3) to Week 24 in:
	- Gait velocity (cm/s) assessed during the 6MWT
	- Stance Time Variability assessed during the 6MWT
	- Asymmetry of the swing duration assessed during 6MWT
	- the Mini-BESTest
	- MDS-UPDRS Part III sub-score
	- the results of the PDQ-39
	 Change from Baseline to Week 12 (Visit 3) and to Week 24 (Visit 4) and from Week 12 to Week 24 in the:
	- gait parameters measured by the FeetMe Monitor during the 6MWTs other than ones of the primary and secondary endpoints
	- gait parameters measured by the FeetMe Monitor during remote gait monitoring
	- results of the pain VAS
	- results of the Parkinson Disease Sleep Scale 2 (PDSS2)
	- results of the Clinical and Patient Global Impression of Severity scales (CGI/PGI-S)
	- results of the Clinical and Patient Global Impression of Improvement scales (CGI/PGI-I)
	• results of the MDS-UPDRS I, II and IV sub scores
	• Actual versus prescribed time spent on physiotherapy at Week 12 and Week 24.
· · · · · · · · · · · · · · · · · · ·	

	• Results of the Patient and Investigator satisfaction questionnaire.
	• Number of device and protocol procedure related adverse events at Week 12 and at Week 24.

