6.2 Schedule of Assessments

Table 6.1 Schedule of Assessments

CIP Number 2023-A00150-45 Final version 0.2

CONFIDENTIAL May 2023

			Primary Inter	vention Period		Long Term Intervention Period			
Visit	Screening ¹	Baseline ²	Visit 1	Visit 2	Visit 3	Visit 1.2	Visit 2.2	Visit 4	End of Study Visit
Timepoint	Day 1	Day 1	Week 4	Week 8	Week 12	Week 16	Week 20	Week 24	Week 26
Visit Window	NA	NA	\pm 7 days	\pm 7 days	\pm 7 days	\pm 7 days	\pm 7 days	\pm 7 days	\pm 7 days
Assessments	In-Clinic + Remote	In-Clinic	Remote	Remote	In-Clinic	Remote	Remote	In-Clinic	Remote
						patients	who switch		
ICF	•								
Eligibility Check	•								
Modified Hoehn and Yahr staging	•							•	
MoCA	•								
Medical History & Demographics		•							
Randomisation	•								
Prior Rehabilitation History	•								
Prior- and Concomitant Medication	•			-	•				
6MWT ³		•			•			•	
Ecological remote gait data collection		for 2 weeks after BL			for 2 weeks after V3			for 2 weeks after V4	
Mini-BESTest		•			•			•	
MDS-UPDRS		•			•			•	

CIP Number 2023-A00150-45 Final version 0.2

CONFIDENTIAL May 2023

FOG-Q	•			•			•	
PDSS-2	•	•	•	•	•	•	•	
Pain VAS	•	•	•	•	•	•	•	
PDQ-39	•			•			•	
PDQ-8		•	•		•	•		
CGI-S / PGI-S	•							
CGI-I / PGI-I				•			•	
Satisfaction Questionnaire	•			•			•	
Falls diary								
Conventional Physiotherapy tracking		From ICF to EOS						
AEs								
Adherence				•			•	

ICF: Informed Consent Form; 6MWT: 6 Minutes Walk Test; Mini-BESTest: Mini Balance Evaluation Systems Test; MOCA: Montreal Cognitive Assessment; AEs: Adverse Events; FOG-Q: Freezing of Gait Questionnaire; MDS-UPDRS I, II & III: Unified Parkinson's Disease Rating Scale parts I, II and III; PDQ-39: Parkinson Disease Questionnaire; PDQ-8: Parkinson Disease Questionnaire Short Form; CGI-S/PGI-S: Clinical/Patient Global Impression of Severity; CGI-I/PGI-I: Clinical/Patient Global Impression of Improvement; PDSS-2: Parkinson Disease Sleep Scale 2;

¹A reflection period of fifteen to thirty days must be given to the subject to decide upon their participation.

² BL assessments will take place right after the Screening Visit.

³ Patients on the FeetMe arm will perform weekly 6MWTs as part of their rehabilitation program using the FeetMe Rehabilitation application.

Note: Visit windows are to be calculated compared to the original schedule, not the previous visit

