8.6.2 Modified Hoehn and Yahr staging (mH&Y)

The modified Hoehn and Yahr scale is a standard clinical rating scale, designed to evaluate the progression and level of functional disability associated with Parkinson's disease and Parkinsonism in a clinical setting (Hoehn and Yahr, 1967). The Hoehn and Yahr scale consists of seven stages describing the extent and impact of symptoms (Goetz et al., 2004). The Investigator performs an interview and a medical examination aimed at evaluating the extent of the patient's symptoms and functional disability. The Investigator scores the stage based on the clinical criteria, where a higher stage value indicates more severe symptoms. The Hoehn and Yahr staging takes approximately 15 minutes to complete.

The mH&Y staging will be performed at Screening and at Visit 4 (Appendix N).

8.6.3 The Movement Disorder Society sponsored Revision of the Unified Parkinson's Disease Rating Scale (MDS-UPDRS)

The Movement Disorder Society sponsored Revision of the Unified Parkinson's Disease Rating Scale (MDS-UPDRS) is a comprehensive assessment of the Non-Motor aspects of Experiences of Daily living (nM-EDL), Activities of Daily Living (ADL), motor symptoms and motor complications of Parkinson's Disease (Goetz et al., 2008). The MDS-UPDRS Part I is a clinician rated (question 1-6) and patient self-reported scale (question 7-13) consisting of 13 questions about Non-Motor aspects of daily living; Part II is a patient self-rated scale consisting of 13 questions about ADLs; Part III is a clinician-rated scale consisting of 18 neurological motor examinations and part IV is a clinician rated scale consisting of 6 motor examinations evaluating dyskinesias and motor fluctuations. All sections are scored on a five point interval scale ranging from 0 (absence of impact) to 4 (most severe impact). Part I is administered partly by the Investigator and partly self-reported by the patient or caregiver; Part II and IV are administered by the Investigator. The MDS-UPDRS takes overall approximately 35 minutes to complete.

The MDS-UPDRS will be performed on site at Baseline Visit, Visit 3 and Visit 4 (Appendix M).

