1	=	minime	:	les dyskinésies retentissent sur quelques activités, mais le patient effectue habituellement toutes les activités et participe à toutes les interactions de la vie sociale pendant les périodes dyskinétiques.				
2	=	léger	:	les dyskinésies retentissent sur beaucoup d'activités, mais le patient effectue habituellement toutes les activités et participe à toutes les interactions de la vie sociale pendant les périodes dyskinétiques.				
3	=	modéré	:	les dyskinésies retentissent sur les activités, au point que le patient ne peut effectuer certaines activités et ou ne peut pas participer à certaines activités sociales pendant les épisodes dyskinétiques.				
4	=	sévère	:	les dyskinésies retentissent sur la fonction au point que le patient ne peut effectuer la plupart des activités et ou participer à la plupart des interactions sociales pendant les épisodes dyskinétiques.				
B.	B. FLUCTUATIONS MOTRICES							
4.	3	Durée des	péri	iodes ON _				
Utili	sez F. C	le nombre alculez le p	d'heu ource	ures éveillées provenant de 4.1 et déterminez les heures passées en condition entage. Si le patient a un épisode OFF durant la consultation, vous pouvez vous				

appuyer sur cet état comme référence. Vous pouvez aussi utiliser votre connaissance du patient pour décrire une période OFF typique. De plus, vous pouvez aussi utiliser vos propres compétences d'interprétation pour représenter une période OFF déjà vue auparavant chez le patient, ou leur montrer la fonction OFF typique d'autres patients. Notez le nombre type d'heures OFF, car vous aurez besoin de ce nombre pour compléter le 4.6.

Certains patients atteints de la maladie de Parkinson retirent un bon effet de leurs médications pendant les heures éveillées et nous appelons cela la période ON. D'autres patients prennent leurs médications mais ont encore quelques heures de baisse de régime, de période mauvaise, ralentie ou période de tremblement. Les médecins appellent ces mauvaises périodes, période OFF. Au cours de la semaine précédente, vous m'avez dit auparavant que vous êtes généralement éveilléheures par jour. Durant ces heures éveillées, combien d'heures au total avez-vous habituellement ce type de baisse régime ou épisode OFF (utilisez ce nombre pour vos calculs).

0 = norm	al :	pas de période OFF.
----------	------	---------------------

- 1
 = minime
 :
 >25% du temps éveillé dans la journée.

 2
 = léger
 <td:	:
 de 26% à 50% du temps éveillé dans la journée.

 3
 = modéré
 :

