Pour les épisodes O nombre d' associées à Dans une d'heures d contrôlée. F spasmes d moments de ferait-il ?	patients q FF comprer heures en une dyston question de période Pendant ces louloureux e la journée	ui ont des fluctuations motrices, nent habituellement une dystonie d période OFF (4.3). Parmi ces hei ie et calculez le pourcentage. S'il n'y que je vous ai posé(e)préc mauvaise ou de temps « OFF » périodes mauvaises ou OFF, ave. ? Sur un total de heures de ce durant lesquels ces crampes doulo	déterminez dans quelle proportion des douloureuse? Vous avez déjà déterminé le ures, déterminez combien d'entre-elles sont y a pas de période OFF, notez 0. cédemment, vous dites avoir généralement quand votre maladie de Parkinson est mal z-vous habituellement des crampes ou des tte période mauvaise, si vous ajoutez tous les pureuses apparaissent, combien d'heures cela	
0 = nor 1 = mir 2 = lég 3 = mo 4 = sév	mal : nime : er : déré : vère :	pas de dystonie ou pas de période < 25% du temps en état OFF. de 26% à 50% du temps en état O de 51% à 75% du temps en état O > 75% du temps en état OFF.	OFF. IFF. IFF.	
			1 - total des heures OFF	

2 - total des heures OFF avec dystonie _____ 3 - % de dystonie OFF = ((2/1) x100) _____

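### The MDS-UPDRS form in Appendix M omits all 13 Part II items, although the Part II sub-score is a listed exploratory endpoint

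*Protocol*

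**What the plan says.** Four places in the protocol bear on which parts of the MDS-UPDRS are collected.

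- **Endpoints.** The Synopsis and Table 5.1 both list the "results of the MDS-UPDRS I, II and IV sub scores" among the exploratory endpoints. Table 5.1 places them under change from Baseline to Week 12 and Week 24. The Part III sub-score is a separate secondary endpoint.
- **Section 8.6.3.** All four parts are described. For the second, "Part II is a patient self-rated scale consisting of 13 questions about ADLs". The section then gives timing and form: "The MDS-UPDRS will be performed on site at Baseline Visit, Visit 3 and Visit 4 (Appendix M"). Section 8.6 adds that the clinical scales are completed on paper, that the paper is the source document, and that scores are entered in the eCRF from it.
- **Table 6.1.** The MDS-UPDRS is scheduled at Baseline, Visit 3 and Visit 4. The legend under the table expands the abbreviation as "MDS-UPDRS I, II & III: Unified Parkinson's Disease Rating Scale parts I, II and III", without Part IV.
- **Appendix M.** The form's title says Parts I to IV. It opens with "Partie I : expérience non motrice de la vie quotidienne" (items 1.1 to 1.13). The next part heading, directly after the fatigue item, is "Partie III : examen moteur en ON". Part IV follows and ends the form.

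**The concern.** The endpoint list and the measurement section ask for a sub-score that the protocol's own form cannot produce. Appendix M is the only MDS-UPDRS form the protocol names, and the completed paper form is the source document. A site that follows the plan literally would therefore finish each visit without a single Part II answer.

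Part II is the scale's daily-living section. Its endpoint is a change from Baseline, so a missed Baseline rating removes the change score even if the form is corrected before Week 12. A rating tied to a given visit cannot be reliably reconstructed afterwards.

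This is a mismatch inside the protocol, between an endpoint and the instrument supplied to measure it. It is not a detail that would normally be left to a statistical analysis plan.

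**Working it through.** No sample size, power or test figure is involved. The check is an item count and a comparison of the text.

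**Item count**

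| Part | Items per 8.6.3 | Items on the Appendix M form |
|---|---|---|
| I | 13 | 13 (1.1 to 1.13) |
| II | 13 | 0 |
| III | 18 | 18 (3.1 to 3.18) |
| IV | 6 | 6 (4.1 to 4.6) |
| Total | 13 + 13 + 18 + 6 = 50 | 13 + 0 + 18 + 6 = 37 |

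The difference is 50 − 37 = 13, which is exactly Part II. Each item is scored 0 to 4, so the missing sub-score has a range of 0 to 13 × 4 = 52.

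**Could the gap come from reading the PDF?** The headings of items 3.9 and 3.17 were lost in reading, but the text of both items is still there. For Part II there is neither a heading nor any item text, and Parts I and III adjoin. Loss of a whole 13-item section in this way is unlikely, but the original PDF should be checked.

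**Upper bound on the loss.** If every site used only this form, up to 150 patients × 3 visits = 450 Part II sub-scores would be missing, before allowing for drop-out.

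**Part IV labels**

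- Item 4.3 has a heading about the duration of ON periods. Its instruction reads "Notez le nombre type d'heures OFF, car vous aurez besoin de ce nombre pour compléter le 4.6", score 0 means no OFF period, and the calculation line gives a percentage of OFF time.
- Section C and item 4.6 are headed as ON dystonia. The question asks about OFF time, the top category is "> 75% du temps en état OFF", and the calculation line gives the percentage of OFF dystonia.
- The category for score 1 in item 4.3 reads as above 25%, whereas items 4.1 and 4.6 have below 25%. Taken literally, it would overlap scores 2 to 4 and leave OFF time above 0 and up to 25% without a category. The surrounding text is visibly damaged in reading, so the sign is not reliable evidence.

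**The case against.** The strongest reply is that every operative passage still asks for Part II: section 8.6.3, the endpoint lists and even the Table 6.1 legend. Only the appended copy lacks it. The protocol nowhere says Appendix M is the only form a site may use, a site could hold a complete copy of the scale, and an empty eCRF field might alert someone. This stands as a limit on size. It does not remove the point, because Appendix M is the only form named and nothing shown provides another.

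It is also fair that the consequence is modest. Sections 9.2.6 and 9.5.3 leave these sub-scores to descriptive summary. The PDQ-39, a secondary endpoint, has its own mobility and activities-of-daily-living dimensions, so the domain is not wholly unmeasured.

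A reader might infer three further things that the document does not support:

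- **That the ON headings in Part IV would produce wrong scores.** For example, a patient OFF for 20% of waking time, and so ON for 80%, might be scored 4 instead of 1 on item 4.3. To do that, a rater would have to disregard the instruction, the anchors and the calculation line, all of which point to OFF time. The headings are wrong labels on items whose content corrects them.
- **That the above-25% category is an established error.** In this stretch of damaged text it may be a reading artefact.
- **That section 8.6.3 contradicts itself by calling Part II self-rated and also administered by the Investigator.** Section 8.6.12 uses both descriptions together for the freezing-of-gait questionnaire, so the two are compatible in this protocol.

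**Conclusion.** The point holds in a limited form. Appendix M is presented as the full four-part scale but carries 37 of the 50 items described in section 8.6.3, and the 13 absent items are the whole of Part II. Used alone, the form yields no Part II sub-score at any of the three scheduled visits, and the data could not be recovered.

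It would go too far to say that the Part II endpoint cannot be obtained. Complete loss assumes that sites use only the appended form and that the gap goes unnoticed, and the document establishes neither. The finding also assumes that the printed appendix matches the text as read.

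The affected data are exploratory. The primary endpoint, the key secondary endpoint and the secondary Part III endpoint do not depend on Part II, and all 18 Part III items are on the form. The Part IV headings and the Table 6.1 legend are minor inconsistencies to tidy at the same time.

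**What to change.** Check Appendix M against the original PDF and insert the 13 Part II items between Parts I and III, for use at Baseline, Visit 3 and Visit 4. If any site already holds the form, replace it there too.

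Minor corrections to make in the same edit:

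- Align the headings of item 4.3, and of section C with item 4.6, with the OFF-time instructions and anchors beneath them.
- Add Part IV to the MDS-UPDRS entry in the Table 6.1 legend.
- Check the sign in the score 1 category of item 4.3 against the PDF. Only if it is really printed as above 25%, change it to the below-25% band used in items 4.1 and 4.6.

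The cost is one replacement form and a few words of text. Section 8.6.3 already allows about 35 minutes for the overall scale it describes in four parts, so the stated visit time need not change. No analysis, sample size or testing step is affected.
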